5.0 STUDY PROCEDURES

5.1 Overview of Study Procedures

Refer to **Appendix 1** for a Schedule of Study Assessments.

5.1.1 Baseline Evaluation

The following baseline evaluations will be assessed and recorded on all subjects who provide written informed consent:

- Demographic information and medical history including risk factors
- Pregnancy test within 1 day of the procedure
- Assessment against Inclusion/Exclusion criteria
- Medical clearance before the procedure
- Contrast-enhanced, high resolution vascular CT demonstrating at least 30% of necrotic debris in walled off necrosis
- Quality of life per SF-36 questionnaire

5.1.2 Baseline Demographics and Relevant Medical History

The subject’s demographic information and relevant medical history will be documented in the subject’s source medical record and on the appropriate case report form (CRF). This will include the subject’s:

- Age
- Gender

- Height
- Weight
- Race and Ethnicity Information
- Relevant medical history
- Physical Examination

5.2 Laboratory Tests

Results from the subject's following laboratory tests will be documented in the subject's source medical record and on the appropriate CRF:

- Urine pregnancy test if female of child-bearing age within 1 day of procedure

5.3 Index Procedure

5.3.1 Eligibility

The Investigator will verify informed consent and confirm the subject meets all inclusion / exclusion criteria. The Investigator, or designee, will record in the subject's source medical record that informed consent was verified, and all inclusion / exclusion criteria were confirmed prior to the index study procedure.

5.3.2 Imaging

Current standard of care for diagnosis of WOPN in patients requires contrast enhanced, high resolution vascular CT scan. Imaging should fall within the following characteristics, per the 2012 Revised Atlanta Classification and can be completed up to 2 weeks in advance of the procedure:

- Heterogeneous with liquid and non-liquid density with varying degrees of loculations (some may appear homogeneous)
- Well defined wall
- Location intra-pancreatic and/or extra-pancreatic

5.3.3 Screen Failures

Enrolled subjects failing to meet inclusion / exclusion criteria at the time of index procedure will not be treated with the EndoRotor® device and; therefore, are classified as screen failures. Any baseline study data captured in the CRFs will be collected. Only subjects in whom the EndoRotor® catheter will be followed and study data analyzed.

5.3.4 Index Procedure

The investigators shall follow the technique described by the manufacturer's instructions as provided in the Instructions for Use. Following stent placement and once the clinician determined removal of necrotic debris should be completed, direct endoscopic necrosectomy of the WOPN will be performed within 2 weeks of enrollment with video documentation of the necrotic debris at start of the procedure. For patients with LAMS, a therapeutic gastroscope must be able to pass through the LAMS necessitating a minimum stent diameter to accommodate the gastroscope such as a 15mm. If a LAMS is used, it must be removed within 60 days per manufacturer's labeled instructions for use.

The EndoRotor® will be set-up and used to resect the WOPN. The resection is removes all accessible necrotic debris wherever the endoscope can provide access. No resection is performed on the pancreatic wall during this procedure. Multiple debridement procedures can be performed to remove necrotic tissue as required.

The EndoRotor® is set to either High Speed (1700 RPM) or low speed (1000 RPM) based on user preference and the vacuum is set to between 550 mmHg of negative pressure. The endoscopist will start the EndoRotor® motor using the left foot pedal and will activate the cutting by depressing and holding the right pedal down for as long as he wants to resect. The technique is repeated until the entire gross visible necrotic debris has been removed to present a cavity clear of necrosis.

5.3.5 Procedural Details

Following placement of EUS guided drainage and determination of the subjects meeting I/E criteria a direct endoscopic necrosectomy procedure can be performed at least 2 days following the EUS guided drainage. During the index procedure the EndoRotor® will be set-up and used to resect all visible and accessible necrotic debris. No resection is performed on the pancreatic wall during this procedure. Multiple procedures can be performed to remove necrotic tissue as required.

Details of the subject's index procedure will be documented in the subject's source medical record and on the appropriate CRF, including:

- Date of Procedure
- Method and Type of Sedation
- Verification of resection results
- Time of endoscope insertion and beginning of EndoRotor use
- An estimate of the percent reduction of the necrosis achieved with the EndoRotor based on endoscopic images
- Time the Procedure was Completed (end of EndoRotor use and time endoscope removed)
- Lot and Serial Number of the EndoRotor® console and catheter
- Any Adverse Events

5.3.6 Post-Procedure Evaluations

Subjects will be discharged from the hospital upon satisfactory completion of all post-procedure recovery requirements as defined by the investigational site's standard protocol and satisfactory resolution of subjects WOPN status.

Adverse events will be recorded in the subject's source medical record and on the appropriate CRF as they are observed.

In addition, hospital utilization will be tracked including total days to discharge and number of procedures completed.

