1.2 Background

Acute pancreatitis is defined by sudden inflammation of the pancreatic gland, which functions to make insulin to control blood sugar levels and enzymes for the digestion of food. While the cause of acute pancreatitis can vary greatly among patients, severe cases can lead to development of life threatening complications, such as infected walled-off pancreatic necrosis (WOPN). Pancreatic necrosis is defined when more than 30% of the gland is affected by necrosis with 20% of patients requiring severe clinical course.³ Of the 20%, one third (33.3%) of cases progress to infected necrosis with patient mortality ranging from 15-30%.⁴ Should acute necrotic collections continue to progress, results may lead to the development of WOPN after 4 weeks time.

The EndoRotor has been demonstrated to be a tool for safe and effective removal of pancreatic necrosis - due to its automated mechanical characteristics, which incorporate rotational cutting and suction for tissue removal in one inclusive device. An investigator-led series was completed by [name], [name] et al at Erasmus Medical Center (Rotterdam, Netherlands) utilizing the EndoRotor in necrosectomy procedures to resect WOPN accessed via trans gastric fistulas created by luminal apposing metal stents (LAMS) and plastic stents (2 pig tails). The primary risk includes procedural bleeding and was tracked in the prospective series. While the device is used to resect necrotic tissue in the cavity perforation does not present a risk with no interaction with wall of pancreas and further there was no evidence of bleeding in the series. The EndoRotor demonstrated complete removal of pancreatic necrosis through various anastomosing stents in twenty-three (23) procedures of twelve (12) patients with no incidences of perforation or bleeding. An abstract of this series was accepted for Digestive Disease Week 2018 for poster with presentation and the investigators continue to treat patients for additional outcomes data. A pending manuscript is under peer review where the

authors presented their findings.

The investigators believe the EndoRotor provides a tool for safe and effective means at removal of necrotic debris in WOPN. Using the first series provides initial feasibility to evaluate the EndoRotor in a larger prospective cohort.

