5.4.2 Follow-up Visit 21 Days (± 7 days)

All subjects will return to the clinic for the 21 (+/-7) day visit as determined from the last EndoRotor procedure. Results of the following study procedures will be recorded in the subject's source medical record and on the appropriate CRF:

- CT Scan Imaging: Record results and the percent resolution of necrotic debris in the collection being treated
- Surveillance endoscopy (only if clinically required) whereby physician can use local standard of care to continue to treat the patient if required
- Physical Exam
- SF-36 Questionnaire

All subjects will exit from the study after this visit; however, all subjects should be followed according to the Investigator's clinical standard practice guidelines for safety.

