7.0 STATISTICAL METHODS

7.1 General Principles

While this protocol does specify primary and safety endpoints, these are not meant to define subject and study success. Instead, the results of this evaluation will be used to establish the safety and efficacy profile of the EndoRotor Procedure and to evaluate the effect size for powering future clinical investigations.

Nominal and ordinal variables for each time period will be presented using frequencies and percent of patients in each category. Interval and ratio variables for each time period will be presented using means and standard deviations, median, quartiles, and minimum and maximum. For variables collected at multiple follow-up time periods, tables, which include change from baseline, will be presented at each follow-up visit.

Distributions of each continuous variable will be assessed prior to analysis and examined for normality. Data with interval or ratio scales to be analyzed that are not normally distributed will be analyzed using non-parametric statistics. Statistical tests will be performed using two-sided significance levels of 5% unless otherwise specified.

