7.4.3 Effectiveness Analysis

Effectiveness Analysis will be assessed via the following secondary endpoints:

- Successful clearance of necrosis in the collection being treated during direct endoscopic necrosectomy where success is defined as at least 70% of the necrotic debris in the WOPN cavity is removed based on CT evaluation of the cavity at 21 (+/-7) day follow up visit.
- Assessment of total procedure time to achieve clearance of necrosis for all procedures
- Assessment of adequacy of debridement
- Assessment of total number of procedures to achieve clearance of necrosis
- Assessment of length of hospital stay and utilization
- SF-36 Questionnaire

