7.5 Missing Data

Missing data within this subject cohort is expected to occur at a low rate. All efforts will be made to prevent the occurrence of missing data. Site training and regular monitoring will help to minimize missing data. Due to the sample size and nature of this pilot study, there will be no imputation of missing data. In other words, analyses will be based only on available data.

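### Length of stay has no rule for subjects still in hospital at study exit or who die there; on available data the former are lost and the stay is understated

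*Combined protocol and SAP*

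**What the plan says.** Section 7.4.3 lists "Assessment of length of hospital stay and utilization" among the secondary endpoints used to assess effectiveness, as does Section 4.4. Neither defines it further. The only operational description is in Section 5.3.6: "hospital utilization will be tracked including total days to discharge and number of procedures completed". No starting day is given.

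Four other provisions determine what happens to this variable:

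- **Discharge.** Section 5.3.6 makes it depend partly on "satisfactory resolution of subjects WOPN status", so subjects whose necrosis resolves slowly can be expected to stay longest.
- **End of follow-up.** Section 5.4.2 times the 21 (±7) day visit "as determined from the last EndoRotor procedure" and adds: "All subjects will exit from the study after this visit".
- **Missing values.** Section 7.5 rules out imputation, and "analyses will be based only on available data".
- **Summary.** Section 7.1 has interval and ratio variables "presented using means and standard deviations, median, quartiles, and minimum and maximum". No time-to-event, censoring or competing-event method is named anywhere.

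**The concern.** Days to discharge is a time to an event, and two kinds of subject may not have the event within follow-up. One is still in hospital at the last visit. The other dies in hospital and is never discharged alive. The plan treats the variable as an ordinary measurement, so its only applicable rule for a subject without a value is to leave that subject out.

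For a subject still in hospital, the value is absent because the stay is long. The loss depends on the outcome itself and pulls the summary down. For a death there are at least two readings: omit the subject, or enter the date of death as the end of the stay. They give different answers. Under the second, an early death appears as a short stay, so a bad outcome looks like a good one.

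The endpoint has no hypothesis attached, but it will be used. Section 7.1 says the results will inform the effect size for future studies, and Section 4.7 relies on the data for the benefit-risk profile.

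**Working it through.** The plan states no length-of-stay figure, so there is none to reproduce. The check has four parts.

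**1. When follow-up ends.** Inputs: visit at 21 (±7) days after the last procedure (Section 5.4.2); all procedures within 14 (+7/−0) days (Section 4.2).

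- Single procedure: 21 − 7 = 14 to 21 + 7 = 28 days after index.
- Latest possible exit: 14 + 7 + 21 + 7 = 49 days after index.
- Nominal exit when the 14-day period is used in full: 14 + 21 = 35 days.

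Section 4.2 itself counts follow-up from the first procedure. The protocol summary, Sections 5.4.1 and 5.4.2 and Appendix 1 count from the last, and that is used here.

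**2. Effect of losing subjects still inpatient.** The stay distribution is an assumption: lognormal from index, true median M, log-SD σ of 0.6 to 0.8, with exit at a common day c.

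- Share discharged by exit: F = Φ(ln(c/M)/σ). Share still inpatient: 1 − F.
- Available-data median: M × exp(σ × Φ⁻¹(F/2)).

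Example with M = 20, c = 28, σ = 0.6: ln(1.4)/0.6 = 0.561, so F = 0.713 and 29% are still inpatient. F/2 = 0.356, Φ⁻¹ = −0.368, and the median is 20 × exp(−0.221) = 16.0 days.

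| True median | Exit day | Still inpatient | Available-data median |
|---|---|---|---|
| 10 | 28 | 4–10% | 9.1–9.7 |
| 10 | 35 | 2–6% | 9.4–9.9 |
| 20 | 28 | 29–34% | 14–16 |
| 20 | 35 | 17–24% | 15.6–17.5 |
| 20 | 49 | 7–13% | 17.5–19.0 |

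The mean moves more. For M = 20 and exit at day 28, the true mean M × exp(σ²/2) is 24 to 28 days, and the available-data mean is 15 to 16.

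A simulation let exit vary: 1 to 4 procedures equally likely, exit 14 to 28 days after the last, σ = 0.6. The available-data medians were 9.6 for a true 10 (6% still inpatient), 13.2 for a true 15 (17%) and 16.0 for a true 20 (29%).

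**3. The same effect without a distribution.** If the k longest stays of 30 are dropped, the reported median sits at about 0.5 × (30 − k)/30 of the full cohort. That is the 48th percentile for k = 1, the 45th for k = 3 and the 42nd for k = 5.

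**4. In-hospital deaths.** Assume 15% die, survivors have a median stay of 15.0 days, and both times are lognormal with log-SD 0.6. Omitting deaths gives 15.0. Counting days to death as the stay gives a whole-cohort median of 13.3 if deaths are early (median day 5), 15.0 if timed like discharge, and 16.4 if late (median day 30). Ranking deaths as the worst outcome gives 17.1. Omission can therefore raise or lower the summary.

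A death rule is likely to be needed even at low mortality. At an assumed 3%, the chance of at least one death among 30 is 1 − 0.97³⁰ = 0.60; at 5% it is 0.79.

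**The case against.** The strongest reply is that the design expects discharge before exit. Appendix 1 places the discharge column ahead of the 21-day visit, Section 5.4.2 has subjects coming back to the clinic, and Section 7.5 expects few missing data. Nor does data collection clearly stop at exit. Table 1 in Section 8.3 times the discharge form from discharge, Section 10.5 follows adverse events until resolved or stable, and Section 9.5 puts the final report after outstanding data discrepancies are settled. Some late discharge dates may thus be recovered. This stands as a reason why the number lost could be small. It is not a rule: nothing requires a discharge date to be obtained after exit, and nothing says what to do without one.

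A reader might also infer that in-hospital deaths drop out and that this too shortens the reported stay. The documents do not support that. No section excludes deaths from length of stay, a site could enter the date of death, and part 4 of the working shows that the direction depends on when deaths occur. Nor should the figure in Section 1.2, "patient mortality ranging from 15-30" per cent, be read as a rate for this trial. It is background for infected necrosis, whereas these subjects must be able to tolerate repeated endoscopy and must have medical clearance.

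Finally, this is one of six secondary endpoints in a single-arm study of 30 with no success criterion. That limits the consequence. With no control arm, any benefit to the device arises only through informal outside comparison or later sample-size work.

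**Conclusion.** The gap is real. Length of stay is undefined for subjects still inpatient at exit and for those who die in hospital. Under the available-data rule the first group is lost and the stay is understated; for the second, neither the handling nor the direction of the effect is specified.

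The size cannot be fixed from the documents. On the assumptions shown, it runs from less than one day (true median 10, exit day 28 or 35) to about four to six days (true median 20, exit day 28), and falls to about one to two and a half days if everyone exits at day 49. Exit before day 28, which the windows allow after a single procedure, would increase the loss. These figures assume a lognormal stay counted from index, exit timing unrelated to stay, and no discharge dates recovered after exit.

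The consequence is confined to a descriptive secondary endpoint, but one that feeds the benefit-risk profile and the planning of later studies. The plan should be changed; the trial's conduct is not in question.

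**What to change.** Add a few lines to Section 7.4.3:

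- Define the endpoint as days from the index procedure to discharge alive.
- Censor subjects still inpatient at study exit.
- Treat in-hospital death as a competing event.
- Report the cumulative incidence of live discharge (Aalen-Johansen estimate), with its median if reached.
- State beside it the numbers of in-hospital deaths and of subjects still inpatient at exit.

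The dates needed are already to be collected: procedure dates (Section 5.3.5), discharge data (Section 8.3) and the dates and outcomes of serious adverse events (Section 10.5). No visit or treatment changes. The cost is slightly more analysis work, and the reported stay may be longer. Other methods are defensible. Even a stated rule for each group with both counts beside the summary would expose the problem in 30 subjects, although a mean or median of observed discharges alone would still be too low whenever subjects remain inpatient at exit.

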5.4 Subject Follow-Up

If at any point during post-procedure subject follow-up, a subject's clinical presentation jeopardizes the safety or welfare of the subject, the Investigator should act in the best interests of the subject, utilizing any and all means judged medically necessary.

5.4.1 Follow-Up Scenarios

There are several scenarios with respect to each individual subject's timeline relative to the severity and volume of WOPN requiring direct endoscopic necrosectomy.

Scenario 1 – Adequate removal of necrotic debris at index procedure. The subject undergoes a

treatment and returns in 21 (+/-7) days for follow-up.

Scenario 2 – Removal of necrotic debris requiring a maximum of 4 endoscopic debridement procedures. The subject undergoes additional treatment(s) with a minimum of 2 days between treatments over a 14 (+7/-0) day period based on endoscopic verification that less than 70% of the necrotic debris has been removed. The subject returns in 21 (+/-7) days following the last debridement procedure performed.

5.4.2 Follow-up Visit 21 Days (± 7 days)

All subjects will return to the clinic for the 21 (+/-7) day visit as determined from the last EndoRotor procedure. Results of the following study procedures will be recorded in the subject's source medical record and on the appropriate CRF:

- CT Scan Imaging: Record results and the percent resolution of necrotic debris in the collection being treated
- Surveillance endoscopy (only if clinically required) whereby physician can use local standard of care to continue to treat the patient if required
- Physical Exam
- SF-36 Questionnaire

All subjects will exit from the study after this visit; however, all subjects should be followed according to the Investigator's clinical standard practice guidelines for safety.

5.4.3 Unscheduled Visits

The subject may return to the outpatient clinic or phone the physician for any reason in their judgment, or in the judgment and upon request of the Investigator. Should such visit(s) occur, the Investigator will record all unscheduled visit findings, phone calls, endoscopy and laboratory results in the subject's source medical record and on the appropriate CRF.

5.5 Post Procedure Imaging

Subjects will receive a contrast enhanced, high resolution vascular CT Scan per standard of care at the 21 (+/-7) day follow up visit. The CT will also be used to measure the effectiveness endpoint to validate disease clearance in the collection being treated.

6.0 Risks / Benefits Assessment

6.1 Risks to the Patient

The EndoRotor procedure poses no new risks to the patient than the commonly used mucosal resection techniques. As with all endoscopic resection and ablation devices, the most common risks are perforation and bleeding requiring intervention. Other commonly known risks to direct endoscopic necrosectomy removal include the following:

- Stent dislodgment
- Delayed bleeding occurring after the patient has been discharged requiring hospitalization and intervention
- Undiagnosed perforation resulting in free air in the peritoneum post-procedure

Risks related to endoscopy include:

- Bleeding
- Infection
- Damage to GI tract and surrounding tissue

Risks related to anesthesia include:

- Post operative confusion
- Heart attack
- Pneumonia
- Stroke

These are all common to established mucosal resection / ablation techniques and endoscopists are well practiced in handling these events. There are no additional risks that are particular to the EndoRotor® mechanical resection device.

6.2 Mitigation Measures to Minimize Risk

All efforts will be made to minimize these potential risks by:

- Selection of qualified investigators and a qualified investigational center;
- Training the Investigator(s) on proper technique for EndoRotor® technique;
- Observation of procedures by the Interscope, Inc. and/or clinical personnel;
- Defining clear inclusion/exclusion criteria that ensure only appropriate subjects are enrolled and treated;
- Ensuring that the treatment and follow-up of subjects is consistent with current medical practice;
- Careful monitoring of adverse events, serious adverse events and device malfunctions by an Independent 3-Member Data Monitoring Committee and Interscope, Inc.;
- Scheduled monitoring visits to the investigational site; and
- Regular communication with Investigator(s) and staff.

